4.2 Target lesions (TL)

4.2.1 Documentation of target lesions

A maximum of 5 measurable lesions, with a maximum of 2 lesions per organ (including lymph nodes), representative of all lesions involved should be identified as TL at baseline. Target lesions should be selected on the basis of their size (longest diameter for non-nodal lesions or short axis for nodal lesions), but in addition should be those that lend themselves to reproducible repeated measurements. It may be the case that, on occasion, the largest lesion does not lend itself to reproducible measurement in which circumstance the next largest lesion, which can be measured reproducibly, should be selected.

The site and location of each TL should be documented as well as the longest diameter for non-nodal lesions (or short axis for lymph nodes). All measurements should be recorded in millimeters. At baseline the sum of the diameters for all TL will be calculated and reported as the baseline sum of diameters. At follow-up visits the sum of diameters for all TL will be calculated and reported as the follow-up sum of diameters.

Special cases:

- For TL measurable in 2 or 3 dimensions, always report the longest diameter. For pathological lymph nodes measurable in 2 or 3 dimensions, always report the short axis.
- If the CT/MRI slice thickness used is > 5mm, the minimum size of measurable disease at baseline should be twice the slice thickness of the baseline scan.
- If a lesion has completely disappeared, the longest diameter should be recorded as 0 mm.
- If a TL splits into two or more parts, then record the sum of the diameters of those parts.
- If two or more TL merge then the sum of the diameters of the combined lesion should be recorded for one of the lesions and 0 mm recorded for the other lesion(s).
- If a TL is believed to be present and is faintly seen but too small to measure, a default value of 5 mm should be assigned. If an accurate measure can be given, this should be recorded, even if it is below 5mm.
- If a TL cannot be measured accurately due to it being too large, provide an estimate of the size of the lesion.

- When a TL has had any intervention eg, radiotherapy, embolisation, surgery etc, during the study, the size of the TL should still be provided where possible.

4.2.2 Evaluation of target lesions

This section provides the definitions of the criteria used to determine objective tumour visit response for TL.

Table 2 Evaluation of target lesions

Complete Response (CR)	Disappearance of all target lesions since baseline. Any pathological lymph nodes selected as target lesions must have a reduction in short axis to < 10 mm.
Partial Response (PR)	At least a 30% decrease in the sum of the diameters of TL, taking as reference the baseline sum of diameters
Stable Disease (SD)	Neither sufficient shrinkage to qualify for PR nor sufficient increase to qualify for PD
Progressive Disease (PD)	At least a 20% increase in the sum of diameters of target lesions, taking as reference the smallest sum on study (this includes the baseline sum if that is the smallest on study). In addition to the relative increase of 20%, the sum must also demonstrate an absolute increase of at least 5 mm.
Not Evaluable (NE)	Only relevant if any of the target lesions were not assessed or not evaluable or had a lesion intervention at this visit. Note: If the sum of diameters meets the progressive disease criteria, progressive disease overrides not evaluable as a target lesion response

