5. STUDY CONDUCT

5.1 Restrictions during the study

Contraception

Patients of child bearing potential and their partners, who are sexually active, must agree to the use of two highly effective forms of contraception throughout their participation in the study and for 3 months after last dose of study drug(s).

- Condom with spermicide
- and one of the following
- oral contraceptive or hormonal therapy (e.g. hormone implants)
- Placement of an intra-uterine device (see [Appendix D](#) as consideration should be given to the type of device/system used)

[Appendix D](#) provides details of acceptable birth control methods to be used within the study.

Other Concomitant treatment

1. No other chemotherapy, hormonal therapy (hormone replacement therapy is acceptable) or other novel agent is to be permitted during the course of the study for any patient (the patient can receive a stable dose of corticosteroids during the study as long as these were started at least 4 weeks prior to treatment, as per exclusion criteria above). Palliative radiotherapy is allowed for pre-existing small areas of painful metastases that cannot be managed with local or systemic analgesics as long as no evidence of disease progression is present (see section [5.6.3](#)).
2. Patients with hormone-refractory prostate cancer may continue to take LHRH agonist treatment during the study if, in the investigator's opinion, this is appropriate.

3. Live virus and bacterial vaccines should not be administered whilst the patient is receiving study medication and during the 30 day follow up period. An increased risk of infection by the administration of live virus and bacterial vaccines has been observed with conventional chemotherapy drugs and the effects with olaparib are unknown.
4. Patients should avoid concomitant use of drugs, herbal supplements and/or ingestion of foods known to modulate CYP3A4 enzyme activity and drugs that are known to be CYP3A4 substrates (see Section 5.6.1) from the time they enter the screening period until 30 days after the last dose of study medication. In vitro data have shown that the principal enzyme responsible for the formation of the 3 main metabolites of olaparib is CYP3A4 and consequently, although the contribution of metabolic clearance to total drug clearance in man is currently unknown this restriction is required to ensure patient safety.

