Table 3 Dose reductions for olaparib

Reduction	Dose Level^a
Initial Dose Level	400 mg bd
1 st dose reduction due to NCI-CTCAE grade 3 or 4 treatment-related SAE/AEs	200 mg bd
2 nd dose reduction due to NCI-CTCAE grade 3 or 4 treatment-related SAE/AEs	100 mg bd
NCI-CTCAE grade 3 or 4 treatment-related SAEs/AEs	No reduction allowed – withdraw patient

^a olaparib must not be decreased below 100 mg bd

Olaparib should be stopped before surgery and restarted following recovery. No stoppage of olaparib is required for any biopsy procedures.

Olaparib should be discontinued for a minimum of 7 days before a patient undergoes therapeutic radiation treatment. This is not required where palliative doses are used.

If new or worsening pulmonary symptoms (eg, dyspnoea) or radiological abnormality occurs, an interruption in olaparib dosing is recommended and a diagnostic workup (including a high resolution CT scan) should be performed, to exclude pneumonitis. Following investigation, if no evidence of abnormality is observed on CT imaging and symptoms resolve, then olaparib treatment can be restarted, if deemed appropriate by the investigator. If significant pulmonary abnormalities are identified, these need to be discussed with the AstraZeneca Study Delivery Physician.

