2. DEFINITION OF MEASURABLE, NON-MEASURABLE, TARGET AND NON-TARGET LESIONS

Patients with at least one lesion (measurable and/or non-measurable) that can be accurately assessed by CT/MRI at baseline and follow up visits should be included in this study.

Measurable: A lesion, not previously irradiated, that can be accurately measured at baseline as ≥ 10 mm in the longest diameter (except lymph nodes which must have short axis ≥ 15 mm) with computed tomography (CT) or magnetic resonance imaging (MRI) and which is suitable for accurate repeated measurements.

Non-measurable: All other lesions, including small lesions (longest diameter <10 mm or pathological lymph nodes with ≥ 10 to <15 mm short axis at baseline*).

Truly non-measurable lesions include the following: bone lesions, leptomeningeal disease, ascites, pleural/pericardial effusion, inflammatory breast disease, lymphangitic involvement of skin or lung, abdominal masses/abdominal organomegaly identified by physical examination that is not measurable by CT or MRI.

Previously irradiated lesions**

Skin lesions assessed by clinical examination***

Brain metastasis***

* Nodes with <10 mm short axis are considered non-pathological and should not be recorded or followed as NTL.

**Localised post-radiation changes which affect lesion sizes may occur. Therefore, lesions that have been previously irradiated will not be considered measurable and must be selected as Non-Target Lesions (NTL) at baseline and followed up as part of the NTL assessment.

Special Cases:

- Lytic bone lesions or mixed lytic–blastic lesions, with identifiable soft tissue components, can be considered measurable if the soft tissue component meets the definition of measurability. Blastic lesions are considered non-measurable.

- Cystic metastases can be considered measurable lesions if they meet the criteria for measurability from a radiological point of view, but if non-cystic lesions are present in the same patient, these should be selected as target lesions.

Target lesions: A maximum of 5 measurable lesions (with a maximum of 2 lesions per organ), representative of all lesions involved suitable for accurate repeated measurement, should be identified as target lesions (TL) at baseline.

Non-Target lesions: All other lesions (or sites of disease) not recorded as TL should be identified as NTL at baseline.

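### Read literally, Appendix C makes a treated target lesion not evaluable only at the visit of the intervention, so later shrinkage from local treatment can count as PR or CR

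*Protocol*

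**What the plan says.** **Not-evaluable rule.** Appendix C section 4.2.2, Table 2 defines NE for target lesions as "Only relevant if any of the target lesions were not assessed or not evaluable or had a lesion intervention at this visit". The words that matter here are "had a lesion intervention at this visit". A note adds that PD overrides NE when the sum meets the PD criteria.

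**Recording rule.** Appendix C section 4.2.1 covers any intervention during the study, naming radiotherapy, embolisation and surgery, and says "the size of the TL should still be provided where possible". It also says "If a lesion has completely disappeared, the longest diameter should be recorded as 0 mm", with no exception for a lesion that was removed. The follow-up sum is taken over all target lesions.

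**Programmed derivation.** Section 11.1 assigns visit responses by program. With up to one third of lesions missing, the sum is scaled up. With more missing, the response is NE unless PD is met. CR is not allowed when any target-lesion data are missing. The trigger is a missing size, and interventions are not mentioned.

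**Local treatment on study.** Section 5.1 states "Palliative radiotherapy is allowed for pre-existing small areas of painful metastases that cannot be managed with local or systemic analgesics" and refers the reader to section 5.6.3, which speaks of bony metastases present at baseline. Section 5.5.6 adds "Olaparib should be stopped before surgery and restarted following recovery". Section 5.6.4 bars other concurrent anti-cancer therapy.

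**Endpoints.** Tumour response (11.1.1) counts confirmed responses before progression or subsequent anti-cancer therapy. ORR (11.1.2) mentions only progression.

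**The concern.** Table 2 ties the NE status to a single visit. A treated lesion with a recorded size is not missing, so nothing in section 11.1 removes it from the sum at later scans. PR is judged on the whole sum against baseline, so shrinkage caused by a local procedure is counted together with any drug effect. Confirmation at least 4 weeks later does not remove the error, because local shrinkage usually lasts.

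This is a single-arm study with response as the primary variable. It has no control group in which the same error would appear, and some tumour groups are planned at about 20 patients. The same sum also defines progression, so PFS, DOR and DCR are exposed as well.

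**Working it through.** The protocol gives no figure to reproduce, and section 12.3 states that no formal sample size calculation was done. The check applies the written rules to assumed lesion sets.

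**Inputs from the protocol.** PR is a fall of at least 30% from the baseline sum. PD is a rise of at least 20% and at least 5 mm from the smallest sum. Scaling applies if at most one third of lesions are missing. A faintly visible lesion too small to measure is entered as 5 mm. **Assumed:** the lesion sizes, and no change in the untreated lesions unless stated.

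**Condition for a false PR.** With the other lesions unchanged, the change in the sum is -(treated lesion's share of the baseline sum) x (its fractional shrinkage). A false PR needs this product to reach 30%.

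**Worked example.** Lesions 40+30+20 = 90 mm; the 40 mm lesion is irradiated to 10 mm.
- As written, at a later scan: (10+30+20-90)/90 = -33.3%, which is PR. Check: 40/90 x 30/40 = 33.3%.
- Untreated lesions only: (50-50)/50 = 0%, which is SD. One of three lesions is missing, so section 11.1 scales: 50 x 90/50 = 90 mm, 0%.

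**Other assumed sets.**

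| Baseline (mm) | Treated lesion | Sum (mm) | Change | As written | Treated as missing |
|---|---|---|---|---|---|
| 40+30+30 | 40 to 0 | 100 to 60 | -40% | PR | SD |
| 40+30+30 | 40 to 5 | 100 to 65 | -35% | PR | SD |
| 30+30+20+20 | 30 to 0 | 100 to 70 | -30% | PR | SD |
| 30+30+20+20 | 30 to 5 | 100 to 75 | -25% | SD | SD |
| 3 x 20 | 20 to 0 | 60 to 40 | -33.3% | PR | SD |
| 3 x 20 | 20 to 5 | 60 to 45 | -25% | SD | SD |
| 4 x 20 | 20 to 0 | 80 to 60 | -25% | SD | SD |
| 5 x 20 | 20 to 0 | 100 to 80 | -20% | SD | SD |
| single 30 | 30 to 0 | 30 to 0 | -100% | target CR | NE |
| single 30 | 30 to 5 | 30 to 5 | -83.3% | PR | NE |

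Not every intervention creates a responder. The error needs a treated lesion that carries much of the sum.

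**Progression can be hidden too.** In the worked example, let the untreated lesions then grow from 50 to 60 mm. The full sum goes from 60 to 70 mm, 10/60 = +16.7%, not PD. The scaled sum goes from 90 to 60 x 90/50 = 108 mm, 18/90 = +20%, which is PD.

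**Weight of one false responder (exact 95% CI).**
- Group of 20: 0/20 = 0% (0 to 16.8%); 1/20 = 5.0% (0.1 to 24.9%).
- All 150: 1/150 = 0.7 points.

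**The case against.** **The visit wording may mean a continuing status.** It can be read as closing the whole list and describing each lesion's state at each visit. Procedures rarely take place at an imaging visit, section 4.2.1 speaks of interventions at any time during the study, and the size it requests has a use in the PD override. That reading is possible. The text does not state it, however, and section 11.1 gives a program nothing to act on. An SAP could settle the matter, but it would have to add to or depart from the rule written here.

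**The route is narrow.** This stands. Section 5.1 refers to section 5.6.3, which speaks of bone, and bone lesions are target lesions only with a measurable soft-tissue component. Section 5.5.6 concerns surgery in general and does not mention resecting a target lesion. As written, a false response would usually need NE, then PR, then a confirming scan without progression, in refractory disease.

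**Guards exist.** A reader might infer that any local treatment would be credited to olaparib in the primary endpoint. The documents do not support that. Section 5.6.4 and the subsequent-therapy clause in 11.1.1 may exclude embolisation or resection, depending on how these are classed. Palliative radiotherapy, which is expressly permitted, is not classed as subsequent therapy anywhere, and ORR has no such clause.

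**The irradiation rule.** A reader might also infer that Appendix C contradicts itself, since section 2 says "lesions that have been previously irradiated will not be considered measurable". That rule governs lesion selection at baseline. It shows that the authors recognised the bias, but for lesions treated on study it is only an analogy.

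**Conclusion.** The point holds as a defect in a stated rule. Followed literally, Table 2, section 4.2.1 and section 11.1 together let a locally treated target lesion count in the sum at later scans, and this can yield a confirmed false PR or CR. ORR is the most exposed endpoint. Tumour response is exposed mainly through permitted palliative radiotherapy.

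The size per case is 5 percentage points in a group of 20 and 0.7 points in 150. The number of cases cannot be estimated, because the protocol gives no frequency for such interventions; it may be zero. The overall rate would therefore move little, and the practical risk lies in the small tumour groups. The lesion sizes and the degree of shrinkage in the examples are assumptions. The conclusion about the rule does not depend on them, but whether a given patient becomes a responder does.

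**What to change.** Leave the existing Table 2 wording on lesions not assessed or not evaluable as a per-visit rule. Add one separate sentence to Table 2 and to section 11.1, for example:

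*A target lesion that has had an intervention (radiotherapy, embolisation, surgery) is treated as missing at that and every later visit. The one-third scaling rule of section 11.1 applies (scaled if no more than one third of lesions are affected, otherwise NE), CR is not allowed, and PD on the recorded sum still takes precedence.*

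Apply it to tumour response, ORR, DOR, DCR and PFS. Reconcile the radiotherapy sites described in sections 5.1 and 5.6.3.

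A shorter edit, extending the visit phrase in Table 2 to any earlier visit, should be avoided. It would also govern lesions not assessed or not evaluable, so one missed lesion would make every later visit NE. It would also leave Table 2 giving NE where section 11.1 scales.

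The cost is one sentence in two places and a change to the derivation program. The downside is that a few visits become scaled or NE, and a patient whose only target lesion is treated can no longer be shown to respond.

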4.3 Non-Target lesions (NTL)

4.3.1 Evaluation of non-target lesions

All other lesions (or sites of disease) not recorded as TL should be identified as NTL at baseline. Measurements are not required for these lesions, but their status should be followed at subsequent visits. At each visit an overall assessment of the NTL response should be recorded by the Investigator. This section provides the definitions of the criteria used to determine and record overall response for NTL at the investigational site at each visit.

Table 3 Evaluation of Non-Target Lesions

Complete Response (CR)	Disappearance of all non-target lesions since baseline. All lymph nodes must be non-pathological in size (<10 mm short axis).
Non CR/Non PD	Persistence of one or more NTL
Progression (PD)	Unequivocal progression of existing non-target lesions. Unequivocal progression may be due to an important progression in one lesion only or in several lesions. In all cases the progression MUST be clinically significant for the physician to consider changing (or stopping) therapy.
Not Evaluable (NE)	Only relevant when one or some of the non-target lesions were not assessed and, in the Investigator's opinion, they are not able to provide an evaluable overall non-target lesion assessment at this visit. Note: For patients without target lesions at baseline, this is relevant if any of the non-target lesions were not assessed at this visit and the progression criteria have not been met.

To achieve 'unequivocal progression' on the basis of non-target lesions, there must be an overall level of substantial worsening in non-target disease such that, even in presence of SD or PR in target lesions, the overall tumour burden has increased sufficiently to merit discontinuation of therapy. A modest 'increase' in the size of one or more non-target lesions is usually not sufficient to qualify for unequivocal progression status.

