11.1.1 Primary Endpoint

Tumour Response

Patients who have a confirmed CR or PR prior to progression or commencement of subsequent anti-cancer therapies will be classified as responders for the primary endpoint, tumour response. Tumour Response is defined as the percentage of patients who are responders.

A confirmed response of CR/PR means that a response of CR/PR is recorded at one visit and confirmed by repeat imaging at least 4 weeks later with no evidence of progression between confirmation visits.

Patients with measurable disease at baseline will be considered to have a visit response if they meet the visit response criteria for CR or PR. Patients with non-measurable disease at baseline will only be considered to have a visit response if they meet the visit response criteria for CR.

A visit response of CR is defined when all target and non-target lesions present at baseline have disappeared (with the exception of lymph nodes which must be < 10 mm to be considered non-pathological) and no new lesions have developed since baseline. A visit response of PR is defined when the sum of diameters of the TLs has decreased by 30% or more compared with baseline (with no evidence of progression) and the NTLs are at least stable with no evidence of new lesions.

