4.6 Evaluation of Overall Visit Response

The overall visit response will be derived using the algorithm shown in [Table 4](#).

Table 4 Overall Visit Response

Target lesions	Non-Target lesions	New Lesions	Overall response
CR	CR	No	CR
CR	NA	No	CR
NA	CR	No	CR
CR	Non CR/Non PD	No	PR
CR	NE	No	PR
PR	Non PD or NE	No	PR
SD	Non PD or NE	No	SD
NA	Non CR/Non PD	No	SD (Non CR/Non PD)
NE	Non PD or NE	No	NE
NA	NE	No	NE
PD	Any	Yes or No	PD
Any	PD	Yes or No	PD
Any	Any	Yes	PD

CR = complete response, PR = partial response, SD = stable disease, PD = progressive disease, NE = not evaluable, NA = not applicable (only relevant if there were no TL/NLs at baseline).

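### Appendix C and 11.1.1 have no rule for disease that reappears after a complete response, so a relapse scan in measurable disease can be coded PR and confirm the response

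*Protocol*

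**What the plan says.** Section 11.1 has visit responses assigned by program, from disease status against baseline and earlier assessments. Appendix C 4.6 fixes the algorithm: "The overall visit response will be derived using the algorithm shown in" Table 4. There is no central review (Appendix C section 6), and 12.2 bases efficacy on the investigator's RECIST data.

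- **Target lesions (Appendix C 4.2.2, Table 2).** PR is "At least a 30% decrease in the sum of the diameters of TL, taking as reference the baseline sum of diameters". PD is "At least a 20% increase in the sum of diameters of target lesions, taking as reference the smallest sum on study", and in addition "the sum must also demonstrate an absolute increase of at least 5 mm". CR needs every target lesion gone and target nodes below 10 mm.
- **Recording (4.2.1).** "If a lesion has completely disappeared, the longest diameter should be recorded as 0 mm". For a lesion faintly seen but too small to measure, "a default value of 5 mm should be assigned"; an accurate measurement below 5 mm is recorded as it is.
- **Non-target lesions (4.3.1, Table 3).** Non CR/Non PD is "Persistence of one or more NTL". PD requires unequivocal progression of existing lesions, with substantial overall worsening.
- **New lesions (4.4).** A new lesion is progression. The return of a baseline lesion is not mentioned.
- **Overall response (4.6, Table 4).** Target CR with non-target Non CR/Non PD is PR. With no target lesions, Non CR/Non PD is SD.
- **Confirmation (11.1.1).** A CR or PR must be "confirmed by repeat imaging at least 4 weeks later with no evidence of progression between confirmation visits". Patients with non-measurable disease respond only by CR.
- **PFS and DOR (11.1.2).** Both end at RECIST progression or death. DOR is confined to measurable disease.

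**The concern.** No row, footnote or sentence says which visit responses may follow an overall CR. When disease that had gone is seen again, the tables can return PR. Because 11.1.1 accepts CR and PR alike at both scans, the scan that shows the relapse can be the one that confirms the response. The patient then counts as a responder in the primary endpoint, and PFS and DOR run on to a later scan. If the investigator calls the same finding unequivocal progression, or a non-nodal target lesion is 1 mm larger (5 mm rather than 4 mm), the patient has a PFS event at that scan and the CR is unconfirmed. In a single-arm, investigator-assessed trial the default coding favours olaparib.

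**Working it through.** The protocol states no figure that depends on this rule, so there is nothing to reproduce. The check applies Tables 2 to 4 and 11.1.1 to scans that follow an overall CR.

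**Target-lesion formulas (Table 2).** PD if (current − smallest) ≥ 5 mm and (current − smallest)/smallest ≥ 20%. PR, absent PD, if (baseline − current)/baseline ≥ 30%. After a smallest sum of 0 mm the percentage increase is undefined; I take it as exceeding 20%, so the 5 mm test decides.

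| Scan after CR (non-target lesions still CR) | Change from baseline | Change from smallest | Table 2 and Table 4 |
|---|---|---|---|
| Non-nodal, 60 → 0 → 4 mm | (60 − 4)/60 = −93% | +4 mm | PR |
| Non-nodal, 60 → 0 → 5 mm | (60 − 5)/60 = −92% | +5 mm | PD |
| One node, 20 → 9 → 13 mm | (20 − 13)/20 = −35% | +4 mm, 4/9 = +44% | PR |
| One node, 20 → 9 → 14 mm | (20 − 14)/20 = −30% | +5 mm, 5/9 = +56% | PD |
| Two nodes, 16+16 → 9+9 → 11+11 mm (sums 32, 18, 22) | (32 − 22)/32 = −31% | +4 mm, 4/18 = +22% | PR |

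The lesion sizes are illustrative. In both nodal PR rows every node is back above the appendix's 10 mm limit for a non-pathological node, and only the 5 mm rule prevents PD.

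**Non-target lesion returns, target lesions still CR.**
1. It was present at baseline, so 4.4 does not make it a new lesion.
2. It is PD only if judged unequivocal progression.
3. Otherwise CR does not apply, NE does not apply because the lesion was assessed, and Non CR/Non PD is what remains.
4. Table 4 then gives PR.

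**Consequence under 11.1.1.** CR at week 8 followed by any of these PR visits at week 16 is CR then PR, 8 weeks apart, with no progression recorded between. That meets the confirmation rule. PFS and DOR continue.

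**No target lesions.** The same return is SD (Non CR/Non PD). It cannot confirm a response, and these patients are outside DOR. Only PFS continues.

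**Size of one patient.** 1/150 = 0.67 points; 1/20 = 5.0 points. With illustrative counts and exact binomial 95% intervals:
- 5/20 = 25.0% (8.7 to 49.1) becomes 4/20 = 20.0% (5.7 to 43.7).
- 40/150 = 26.7% (19.8 to 34.5) becomes 39/150 = 26.0% (19.2 to 33.8).

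**How many patients.** The protocol gives no CR rate. If 2% to 6% of 150 reach CR (3 to 9 patients) and one third first relapse by one of these routes, 1 to 3 patients are affected. Both proportions are assumptions. The primary endpoint moves only for those whose first scan after CR is the relapse, which may be none, so the range there is 0 to 3 patients, or 0 to 2.0 points of 150.

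**The case against.** The strongest reply is that the non-target case is silent rather than miscoded. Persistence does not literally describe a lesion that went away and came back. Table 3 allows an important progression in a single lesion to count as unequivocal, so the investigator may call PD. The PR definition in 11.1.1 also requires non-target lesions to be at least stable, and a returned lesion arguably is not. Section 6.3.2 already covers doubt about non-target progression: reassess and, if confirmed, date progression at the first scan. All of this stands. It means that the outcome is left to judgement, not that the PR coding is excluded: Table 4 has no stability test for target CR with Non CR/Non PD, and back-dating applies only where the investigator raises a doubt.

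A second reply is that the 5 mm rule exists to stop small fluctuations from being called progression, and that in the two-node example the sum is at least 30% below baseline at both scans, so a response call is consistent with the definition. That is fair, and it makes the target-lesion part the smaller one. It does not settle whether nodes back above the appendix's own size limit should confirm a CR.

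A third reply is that sequencing rules belong in the statistical analysis plan. Here the protocol fixes the algorithm and the confirmation rule itself, so a plan that recoded these visits would depart from Table 4.

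A reader might infer something stronger: that the tables ignore earlier visits and generally turn relapse after CR into a confirmed response. The documents do not support that. Table 2 measures progression from the smallest sum on study; non-nodal target regrowth of 5 mm or more, including the 5 mm default for a faint lesion, is already PD; and patients without target lesions cannot be confirmed this way.

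**Conclusion.** The gap is real and reaches the primary endpoint, but by a narrow route: measurable disease, an overall CR, and then either a returning non-target lesion not called unequivocal progression or target or nodal regrowth of less than 5 mm. There the stated tables can give PR, that PR can confirm the CR, and PFS and DOR do not end. In patients without target lesions only PFS is exposed.

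The effect on the overall rate is probably small and cannot be estimated from the protocol. The trial is exploratory, with no response threshold to cross. The reason to act is that the direction favours the drug and that one patient matters in a tumour-type group of the intended minimum of 20. A claim that the overall response rate is materially inflated would go beyond the documents.

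**What to change.** Add a footnote to Appendix C Table 4 and a matching sentence to 11.1 and 11.1.1, worded for the derived response used in analysis:

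- After an overall visit response of CR, only CR, NE or PD may be derived.
- Unequivocal reappearance of baseline target or non-target disease (for a node, short axis back to 10 mm or more) is derived as PD at that scan and does not confirm a response.
- Doubtful reappearance follows the existing repeat-scan and back-dating rule in 6.3.2 and Appendix C 4.4.

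The cost is a few lines of text and of derivation code, with no extra scans. The downside is that after a CR the derivation would override the 5 mm rule, so small nodal fluctuations around 10 mm could be coded PD; the repeat-scan rule limits this. Because objective progression is also a reason to stop treatment, the sponsor should reconcile the wording with 3.1, 5.5.2 and 5.8. This point takes no position on what those treatment passages should say.
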